The detailed sample size calculation for each study outcome is attached in Appendix B. The required sample size is based on the requirements for the development and validation of the least common DM complication of ESRD. Specifically, based on our previous study, the 5-year incidence of ESRD was 1.9%(8), which can be extrapolated to a 10-year incidence of ESRD was 3.8% by assuming a constant incidence rate over time. To develop the risk prediction model for ESRD by multivariable Cox proportional hazard regressions with forward stepwise variables selection on 16 potential risks factors, we need 21,053 subjects using the 1 in 50 rule that 1 candidate predictor can be studied for every 50 events (23). To validate the risk prediction models, the area under the receiver operating characteristic curve (AUC) will be used to assess the discriminatory power of the predictive model on a separate sample of subjects. With 10 years incidence rate of ESRD was 3.8%(8), a total 14,307 subjects (544 subjects with ESRD and 13,763 subjects without ESRD) is needed to

ensure a precision of 0.05 for AUC of 0.7 by a 95% confidence interval.

Hence, a total 35,360 male and 35,360 female are needed for the development (training dataset) and validation of risk prediction models stratified by gender. The HA data set that we have obtained for our 5-year evaluation of quality of care and effectiveness of RAMP-DM study(8) has identified 120,857 DM patients under the care of public primary care on or before 1 Jan 2009, so we should be able to obtain sufficient number of subjects.

(iii) **Methods**

Each patient will be followed from 1 July 2006 to 31 December 2016 for the development of the indicator DM complications and mortality.

Definition of indicator DM complications

The incidence of four major DM complications (CHD, stroke, heart failure and ESRD), total CVD and all-cause mortality will be calculated. The incidence is counted from the earliest date of documented diagnosis defined by the relevant ICPC-2 and/ or ICD-9-CM coding recorded in the HA CMS database from 1 July 2006 to 31 December 2016. The relevant ICPC-2 and ICD-9-CM codes of each DM complication and mortality are determined by the academic and HA clinician co-investigators as listed below:-

1. CHD (ischaemic heart disease, myocardial infarction (MI), coronary death or sudden death) is defined by any of ICPC-2 K74 to K76 and ICD-9-CM 410.x, 411.x to 414.x, 798.x

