3. 10-year risk prediction models for total CVD, all-cause mortality and each of 4 major DM complications
4. Factors that have sufficient power to classify Chinese DM patients in primary care into risk group in terms of total CVD and all-cause mortality.

(iv) **Data processing and analysis**

The cohort will be stratified by gender. Descriptive statistics will be used to calculate the incidence of total CVD, all-cause mortality and each of 4 major DM complications will be analysed annually and cumulatively over 10 years with a 95% confidence interval. The distribution of risk factors will be cross-tabulated by complication or mortality events. The 10 year cumulative incidence of various DM complications and mortalities will be further analysed by Kaplan-Meier method. The Kaplan-Meier survival curve will be used to describe the survivorship of total CVD, all-cause mortality and each of 4 major DM complications in the study cohort over 10 years. Unadjusted associations between the risk factors and odds of events will be assessed by independent t-test for continuous variables or Chi-square test for categorical variables.

The cohort will be randomly split on a 2:1 basis, with the two-third sample used for developing the risk prediction models, and the other one-third sample used for validation of the risk prediction models. The analyses will be carried out separately for men and women.

Development of risk prediction models

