Cox proportional hazard regressions with forward stepwise method will be used to develop the risk prediction models for total CVD, all-cause mortality and each of 4 major DM complications. If the main term of a clinical parameter is selected in the models, the quadratic term of such clinical parameter will be evaluated. Afterwards, the interaction terms between selected predictors and age will be also examined in the risk prediction models. Cox regressions is the most commonly used method in risk prediction models in the Framingham Heart Study (9, 10) and UKPDS (11, 12). It allows us to estimate the risk of disease or death for an individual, given their prognostic variables. A positive hazard ratio means a higher likelihood of event associated with that specific variable. Conversely, a negative hazard ratio means a lower likelihood of the event associated with that specific variable. The key proportional hazards assumption will be assessed by examining plots of the scaled Schoenfeld residuals against time for the covariates. Any non-random pattern indicates a violation of the proportional hazards assumptions in which case transformation of covariates may be considered. For example, all continuous variables were naturally logarithmically transformed to minimize the influence of extreme values and to

improve discrimination and calibration of the models. A parametric approach such as exponential or Weibull distribution for the hazard function can also be carried out. A total of 6 risk prediction models will be established for total CVD, all-cause mortality and each of 4 major DM complications. The log of the hazard ratio of each selected risk factor in the final model will be used as coefficient weights in the prediction model of each relevant outcome. The risk equations for 10 year's follow-up will be established by combining these weights with the survivor function(9). A receiver operating characteristic (ROC) curve of predicted risk against observed events will be used to determine the risk threshold for the predicted outcomes as the risk threshold with the highest sum of sensitivity and specificity of the actual observed events.

Validation of risk prediction models

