To validate the risk prediction models for total CVD, all-cause mortality and each of 4 major DM complications, they will be applied to the data of the one third validation sample to estimate the risk level of the subjects. A receiver operating characteristic (ROC) curve of predicted risk against observed events will be used to calculate the area under the curve (AUC) for assessing overall prediction accuracy. The corresponding 95% confidence interval will be obtained by bootstrapping of size 2000. An AUC of less than 0.7 indicates limited discriminating power, 0.7 to 0.8 is acceptable, and higher than 0.8 suggests strong discrimination of the predictive models. Using the optimal prediction risk threshold identified by ROC curve in training dataset, and the corresponding sensitivity and specificity of the models against observed events will be calculated to further evaluate the performance of the models.

Calibration will be used to measure how closely predicted outcomes agree with actual outcomes. Calibration of the model's ability to correctly estimate the absolute risks will be examined by modified Hosmer-Lemeshow test and calibration plots. The modified Hosmer-Lemeshow test for time to event data measures how well the predicted probability of the expected event rate agrees with the observed event rate, where a *p*-value higher than 0.05 indicates good model calibration. In a calibration plot of the observed incidence of events against the predicted risk shows the scatter along the 45° line of perfect fit between predicted risk and observed incidence of event throughout the entire risk spectrum.

The D statistic, R^2 statistic and Brier score will be calculated for assessing the predictive power of the model. The D statistic is a measure of discrimination where higher value indicates better discrimination. The R^2 statistic is a measure of explained variation with a higher value indicating better performance. The Brier score is a measure of goodness of fit in which a lower value mean higher accuracy.

Development of a risk prediction nomogram and chart

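### For five of the six models, deaths before the event have no stated handling, so predicted 10-year risk and the outcome used to judge it may not match

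*Combined protocol and SAP*

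**What the plan says.** All references are to the combined protocol and SAP, section d).

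- **Model.** Under Development of risk prediction models: "Cox proportional hazard regressions with forward stepwise method will be used to develop the risk prediction models". Absolute risk is then formed from the coefficients: "The risk equations for 10 year's follow-up will be established by combining these weights with the survivor function".
- **Incidence.** The opening of (iv) states: "The 10 year cumulative incidence of various DM complications and mortalities will be further analysed by Kaplan-Meier method".
- **Validation.** Under Validation of risk prediction models: "A receiver operating characteristic (ROC) curve of predicted risk against observed events will be used to calculate the area under the curve (AUC". Sensitivity and specificity are also taken against observed events, at a threshold chosen on a training-set ROC curve of the same kind. An AUC below 0.7 is labelled limited, and hypothesis 2 in section c) asks for more than 70% discriminating power.
- **Brier score.** It is described only by its direction: "The Brier score is a measure of goodness of fit in which a lower value mean higher accuracy". Whether the form is binary or censoring-weighted is not stated.
- **Calibration.** A survival version is named: "The modified Hosmer-Lemeshow test for time to event data measures how well the predicted probability". How observed risk is estimated is not stated.
- **Follow-up and deaths.** "Each patient will be followed from 1 July 2006 to 31 December 2016 for the development of the indicator DM complications and mortality". Deaths come from the death registry. Coronary and sudden deaths count as CHD events, and fatal strokes as stroke events.

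The document never mentions competing risks. It does not say how a death before CVD, CHD, stroke, heart failure or ESRD enters the model, the ROC curve, the Brier score or the calibration.

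**The concern.** A Cox model that censors other deaths, converted through the survivor function, estimates the 10-year risk that would apply if nobody died of anything else. An ordinary ROC curve on observed events asks whether the event actually happened, and a patient who dies event-free in year 2 naturally falls among the non-events. These are different targets. Everyone shares one start and one end date 10.5 years apart, so administrative censoring cannot fall before year 10. Death is therefore the main reason visible in the plan for incomplete 10-year status.

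Two results are at stake. The first is absolute risk: the charts sort patients into 10-year CVD risk groups at 10% and 20%, and section b) criticises existing models for overestimating risk in this population. The second is the AUC, which is read against 0.7.

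**Working it through.** **1. The plan's own precision (Sample size calculation).** Development: 16 predictors × 50 events / 0.038 = 21,053, as stated. Validation uses the Hanley-McNeil variance with A = 0.70, n₁ = 544 and n₀ = 13,763:

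SE² = [A(1−A) + (n₁−1)(a−A²) + (n₀−1)(b−A²)] / (n₁n₀), where a = A/(2−A) and b = 2A²/(1+A).

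This gives SE = 0.01275 and a 95% interval of ±0.025, full width 0.05. Solving for N gives 14,297 against the stated 14,307. An AUC shift of about 0.025 is therefore as large as the half-width that the study was sized to achieve.

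**2. One patient.** Take constant yearly hazards λ for the event and μ for death without it.

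- Death-removed risk: 1 − exp(−10λ).
- Actual event probability: λ/(λ+μ) × [1 − exp(−10(λ+μ))].

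Assume a death-removed CVD risk of 22% and a 10-year competing death risk of 30%. Then λ = −ln(0.78)/10 = 0.02485 and μ = −ln(0.70)/10 = 0.03567. The actual probability is 0.02485/0.06051 × (1 − 0.78 × 0.70) = 0.4106 × 0.454 = 18.6%. The model puts this patient in the group above 20%, while the actual risk lies in the 10% to 20% group.

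**3. A population.** The same formulas were integrated over a standard normal risk score. The documents give no death rate and no CVD incidence, so the following are assumptions: death-removed risk 20%, death-removed AUC 0.70, and a range of competing death risks and of death hazard ratios per SD of the score.

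| Competing death risk | Death HR per SD | AUC, deaths as non-events | Predicted/actual, mean | Predicted/actual, top decile |
|---|---|---|---|---|
| 10% | 1 | 0.698 | 1.05 | 1.05 |
| 10% | 2 | 0.685 | 1.07 | 1.14 |
| 20% | 0.67 | 0.707 | 1.09 | 1.05 |
| 20% | 1 | 0.696 | 1.11 | 1.10 |
| 20% | 1.5 | 0.681 | 1.14 | 1.21 |
| 20% | 2 | 0.669 | 1.16 | 1.33 |
| 20% | 3 | 0.650 | 1.20 | 1.58 |
| 30% | 2 | 0.653 | 1.26 | 1.56 |

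With the document's 3.8% ESRD risk, a death-removed AUC of 0.70 and 20% competing death, the AUC is 0.708, 0.699, 0.686, 0.674 and 0.655 for HR 0.67, 1, 1.5, 2 and 3. Mean predicted/actual risk is 1.09 to 1.24.

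Starting from an AUC of 0.75 (20% risk, 20% death), HR 2 gives 0.719. Only HR 3 brings it to 0.700.

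**4. Simulation with age as predictor.** CVD risk was set at 20%, with 10% to 26% dying event-free (assumed). Mean predicted/actual risk was 1.08 to 1.28, and 1.10 to 1.85 in the top decile. AUC shifts were 0.01 to 0.06, for example from 0.714 to 0.684.

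**5. A different rule for early deaths.** Assume age SD 11 years, HR per year 1.05 for CVD and 1.09 for death, a second predictor unrelated to death (log-HR 0.5), and 17% event-free deaths. The death-removed AUC is 0.714. Counting deaths as non-events gives 0.683; excluding those patients gives 0.726.

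**6. Brier score.** At 20% death and HR 2, using death-removed instead of actual risk raises it from 0.1352 to 0.1373 (20% risk), or from 0.0305 to 0.0307 (3.8% risk). This is a small effect.

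**The case against.** The strongest reply is that neither handling of deaths is written down. Censoring in the model and non-event status in the ROC curve are the default readings of the named methods, and excluding or weighting the early deaths is not ruled out. That stands: the fault is an unspecified rule, and the mismatch is an inference.

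Second, AUC depends only on ranking, and any score may fairly be tested against actual 10-year status. The threshold and the sensitivity and specificity are at least consistent with each other. This also stands. A reader might infer that the plan biases the AUC downwards, but the documents do not support that. The gap separates two legitimate quantities, almost vanishes when death is unrelated to the score, changes sign when the relation is inverse, and reverses if early deaths are excluded. A positive relation is plausible because age is a candidate predictor, but its strength is unknown. With a strong second predictor (log-HR 1.0) in the setting of step 5, the drop was about 0.019, from 0.799 to 0.780, well clear of 0.7.

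Third, the scope is limited. The mortality model is unaffected, and coronary, sudden and fatal-stroke deaths are already events for the outcomes that include them. Calibration is already planned in a time-to-event form. That last point gives little comfort: if observed risk in that test is a Kaplan-Meier estimate, it shares the model's death-removed scale and would hide the over-prediction.

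**Conclusion.** The concern holds for total CVD, CHD, stroke, heart failure and ESRD, in a limited form. Under the default reading of the named methods, the predicted risks are too high as statements of what will actually happen within 10 years. The factor is about 1.1 to 1.3 on average and larger in the top risk decile, and this bears directly on the 10% and 20% CVD bands. The direction held in every scenario examined; the size rests on assumed death shares, CVD incidence and hazard ratios.

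For the AUC, the supported statement is weaker. The value reported will depend on an unstated rule, by about 0.01 to 0.06 when death risk rises with the score, and this can decide which side of 0.7 a model falls on. A reader might go further and conclude that hypothesis 2 will be wrongly rejected. The documents give neither the death rate nor the expected AUC that such a conclusion needs. The Brier part is minor, and its form is not given. The point should be settled before analysis.

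**What to change.** State one estimand for the five non-mortality outcomes, fix the horizon at exactly 10 years (follow-up runs to 10.5), and apply it to the model, the ROC curve and threshold, the Brier score and the calibration.

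- **Preferred**, because the models are meant to give actual 10-year risk: predict cumulative incidence with death as a competing event, by combining cause-specific Cox models or by Fine-Gray. Count prior deaths as event-free in AUC, sensitivity, specificity, Brier score and calibration. Take observed risk from the Aalen-Johansen estimator, and use it in place of Kaplan-Meier for the descriptive cumulative incidence.
- **If death-removed risk is kept:** say so explicitly. Use Harrell's or Uno's C, or a time-dependent AUC, with a censoring-weighted Brier score. Also report predicted risk against Aalen-Johansen observed risk, overall and by risk decile, so that over-prediction stays visible.

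In either case, report the number dying event-free by sex and outcome. Death dates are already to be obtained, so the cost is SAP wording and a modest amount of code. The reported AUC or risks may look less favourable.

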A key to cost-effective management of DM is an accurate risk assessment and stratification system that identifies high-risk patients for more intensive medical and psychosocial interventions. At the same time, an accurate estimation of risk distribution can inform policy-makers to allocate appropriate resources and plan services that can maximum population health benefit for DM patients. Existing prediction functions commonly used include the Framingham [10-year] (9, 10), the United Kingdom Prospective Diabetes Study (UKPDS) [5-year] (11, 12) and the local (Joint Asia Diabetes Evaluation (JADE) [5-year] (13, 14) models. However, our earlier study on 10,969 diabetic patients managed in the HA primary care clinics showed none of these models was accurate in predicting the observed events over a 4-year follow up for this patient population (15). The Framingham models overestimated the risks of CHD and stroke by 2.0 times and 23%, respectively(15). Several other studies have also concluded that the Framingham models were not applicable to Chinese populations (16). The UKPDS risk prediction models also showed a tendency to overestimate the risk of CHD and stroke by 5.1 times and 51%, respectively (15). The JADE prediction models, although developed from the local Chinese population, overestimated the 4-year CHD, stroke rates by 2.9 times and 41%, respectively, when compared to the actual 4-year observed incidences (15). The JADE prediction models were developed from data of Chinese diabetic patients under specialist care who are more likely have more severe disease and many had complications such as stroke or CHD at baseline (13, 14), which may explain why they tend to over predict complications in primary care DM patients. The

cohort from JADE was collected almost 20 years ago (1995) and the number of subjects (around 7000) was relatively small, which may not be generalizable to the 400,000 DM patients under HA care. Furthermore, JADE only provides 5-year risk prediction although 10-year risk is the international standard (17).

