In order to enable the 10-year risk prediction models for total CVD and all-cause mortality to be applied in busy clinical setting, risk prediction nomograms and charts will be developed for men and women. For the nomogram, the patient's score for each predictor is plotted on the appropriate scale and vertical lines are drawn to the line of points to obtain the corresponding scores. The score of each predictor will be transformed based on the estimated standardized beta coefficient of each predictor from the risk prediction model. For the continuous predictors (e.g. age), the line with interval depends on it units from minimum to maximum values among studies subjects (e.g. 20, 40, 60, 80 years old) will be displayed on the nomogram plot and the corresponding scores will be obtained based on the estimated standardized beta coefficient of the predictor (e.g. assign age of 20 to 0 point, age of 40 to 2 points, age of 60 to 4 points, age of 80 to 6 points). For categorical predictor (e.g. gender), each level of the predictor will be ranked a corresponding score based on the estimated standardized beta coefficient of the predictor (e.g. assign female to 0 point, male to 3 points). We have developed a similar nomogram on the risk of DM in a previous study as shown in Appendix C (24). All scores are summed to obtain a total score. The total score is plotted on the total line with corresponding predicted risk of CVD. Moreover, we will develop risk prediction charts similar to those developed by the Joint British Society as shown in Appendix D. The most significant predictors, up to a maximum of five, found in the full Cox regression models will be selected to classify subjects into 10-year CVD risk groups of <10% (low risk), 10%-20% (medium risk) and >20% (high risk). The Kaplan-Meier survival curves of each risk group will be developed and compared by log-rank tests to confirm the hazard ratios are significantly different among all risk groups.

STATA software version 13 (STATA Corp, College Station, Texas) will be used for data analyses. 5% is used as the level of significance in all statistical tests.

Strategies against anticipated problems

1. Missing data of risk factors

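### A Hosmer-Lemeshow p above 0.05 is read as good calibration, yet at the planned ESRD validation size a 10% error in the hazards would pass in roughly half to three-quarters of validations

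*Combined protocol and SAP*

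**What the plan says.** Under Validation of risk prediction models, absolute-risk accuracy "will be examined by modified Hosmer-Lemeshow test and calibration plots". For the test, a p-value "higher than 0.05 indicates good model calibration". The other element is a "calibration plot of the observed incidence of events against the predicted risk", judged by scatter about the 45-degree line, with no numeric summary. A Brier score is planned without a criterion, and it mixes calibration with discrimination. No observed:expected ratio, calibration-in-the-large or calibration slope is named. The AUC, by contrast, gets graded bands and a bootstrap 95% interval in the same section. The general rule on testing is that "5% is used as the level of significance in all statistical tests".

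The Sample size calculation sets the ESRD validation sample from the precision of the AUC: "a total 14,307 subjects (544 subjects with ESRD and 13,763 subjects without ESRD) is needed". Under Data processing and analysis, "The cohort will be randomly split on a 2:1 basis", and men and women are analysed separately. The rule thus applies to six outcomes in each sex.

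**The concern.** A p-value above 0.05 means only that the data did not contradict the predictions strongly enough. How often that happens for a given error depends on the number of events. The same proportional error can therefore be labelled good for a rare outcome and not for a common one. This rule is the plan's only numeric calibration criterion, and the validation sample was not sized for it.

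The size of absolute-risk error matters to this study. The Introduction justifies new models by the size of over-prediction in existing ones; the local models, for example, "overestimated the 4-year CHD, stroke rates by 2.9 times and 41%, respectively, when compared to the actual 4-year observed incidences". The charts will sort patients at absolute 10-year CVD risks of 10% and 20%. A p-value gives no comparable figure for the new models.

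**Working it through.** **1. Inputs from the plan.** Validation n = 14,307 per sex, ESRD 10-year incidence 3.8%, 544 events, alpha 0.05, AUC 0.7, development n = 21,053, 16 candidate predictors.

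**2. The plan's own figures reproduce.**
- Development: 16 x 50 / 0.038 = 21,053.
- Validation, Hanley-McNeil: A/(2-A) = 0.7/1.3 = 0.5385 and 2A²/(1+A) = 0.98/1.7 = 0.5765. Variance = [0.21 + 543(0.5385 - 0.49) + 13,762(0.5765 - 0.49)] / (544 x 13,763), so SE = 0.01275 and the total 95% width is 2 x 1.96 x 0.01275 = 0.050.
- The sample is therefore sized for AUC precision, not for the calibration test.

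**3. Approximation by hand.** Take ten risk groups and 9 df, so the critical value is 16.92, with no censoring. Pool the error into one non-centrality, (observed - expected)² / [n p (1 - p)], where p is the predicted risk.
- ESRD, true hazards 10% above predicted: expected 14,307 x 0.038 = 543.7; true 14,307 x (1 - 0.962^1.1) = 596.9. Non-centrality = 53.2² / 523.0 = 5.41, and P(p > 0.05) = 0.70.
- ESRD, predicted hazards 10% above true: true 495.1. Non-centrality = 48.6² / 523.0 = 4.51, and P = 0.75.
- Incidence 10% (assumed), hazards 10% above: 1,430.7 against 1,565.7; non-centrality 14.1; P = 0.25.
- Incidence 20% (assumed), hazards 10% above: 2,861.4 against 3,114.0; non-centrality 27.9; P = 0.02.

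**4. Simulation of the time-to-event test.** Each setting has 2,000 validations (Monte Carlo SE about 1 point). Assumptions: normal linear predictor with SD 0.9 (AUC about 0.74-0.75), ten groups, Kaplan-Meier at 10 years in each group, 9 df, and 20% ten-year death treated as censoring. Two variances are used because the plan does not say which modified test it means. The share with p > 0.05 is:

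| Setting | 3.8% (ESRD) | 10% (assumed) | 20% (assumed) |
|---|---|---|---|
| Perfect calibration, Greenwood | 87% | 92% | 93% |
| Perfect calibration, D'Agostino-Nam | 88% | 90% | 88% |
| Hazards 10% above predicted, Greenwood | 77% | 37% | 6% |
| Hazards 10% above predicted, D'Agostino-Nam | 52% | 20% | 2% |
| Hazards 10% below predicted, Greenwood | 50% | 18% | 2% |
| Hazards 10% below predicted, D'Agostino-Nam | 64% | 20% | 2% |
| Full range for a 10% error (0-30% death, second seed) | 46-78% | 14-41% | 0-7% |

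Fixing the true rather than the predicted incidence moves the upper ends to about 42% and 8% in the last two columns. SD 0.75 (AUC about 0.70) gives 77%, 38% and 5% for hazards 10% above, Greenwood. A separate calculation without censoring, using 8 or 9 df, gives 51-76% for ESRD.

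**5. Other sizes of error.**
- Hazards 5% above, Greenwood: 88%, 84% and 67%.
- Hazards 20% above, ESRD: 19% (Greenwood) or 6% (D'Agostino-Nam).
- Over-prediction by 23%: about 4-8% for ESRD and about 0% at 10% and 20% incidence.
- Random-split sampling error only (21,053 development subjects, 16 parameters), Greenwood: 81%, 84% and 85%.

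**6. What a ratio would show.** With hazards 10% above predicted, observed:expected averages 1.10 (95% CI 1.01-1.19), 1.09 (1.04-1.14) and 1.08 (1.04-1.12) at the three incidences. The estimate is nearly the same while the pass rate falls from 77% to 6%. For ESRD, the half-width is about 1.96/√544 = 8.4% on the ratio, or 9 points in the simulated interval. On the slope it is 1.96/(SD x √544), which is 0.09 at SD 0.9 and 0.11 at SD 0.75.

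**The case against.** **Validation is internal.** It uses a random third of the same cohort, so sampling error alone would usually be smaller than 10%. Under that error alone, the pass rates (81%, 84%, 85%) hardly differ between outcomes. This stands, although misspecification was not modelled.

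**The plots carry the missing information.** They show size and direction by eye, and no model selection, recalibration or stopping depends on the p-value. This stands too: the harm is a misleading label and a missing numeric summary.

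**ESRD is the least favourable outcome for the test.** The plan calls it the least common complication, and nomograms and charts are planned only for total CVD and all-cause mortality. With more events, a 10% error is usually detected. The incidences for those outcomes had to be assumed, because Appendix B is not in the text reviewed.

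**The validation size is uncertain.** All eligible patients enter. One third of half of 120,857 is 20,143 per sex, and the ESRD figure for hazards 10% above then falls from 77% to 66% (Greenwood). In the other direction, one third of 35,360 is 11,787, with 11,787 x 0.038 = 448 events. The no-censoring calculation then gives 57-80%.

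**Two stronger readings do not hold.** A reader might infer that the test could not show whether the new models over-predict less than those they replace. The smallest over-prediction in the Introduction is 23%, and an error that large passes in only about 4-8% of validations even at ESRD's incidence. The Introduction's figures concern CHD and stroke, which the plan treats as more common. A reader might also infer that a pass for ESRD says almost nothing. That rests on one near-worst combination (Greenwood, under-prediction, 77% against 87%); D'Agostino-Nam in the same direction gives 52% against 88%.

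**Conclusion.** The rule is wrong as written, because non-rejection does not establish good calibration. The practical weakness concerns moderate errors of about 10%. For ESRD at the planned size, such an error passes in roughly 46-78% of validations, against about 87% with perfect calibration. At assumed incidences of 10% and 20% it passes in about 14-41% and 0-7%. A pass does largely exclude errors as large as those reported for the existing models, but it cannot rank smaller ones or give their direction.

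The figures rest on assumptions that the plan does not fix: ten groups, the degrees of freedom, the variance form, the risk spread, and deaths treated as censoring. The direction holds across all the settings examined. The plan should be changed before analysis, but this does not invalidate the study.

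**What to change.** Delete the statement that p above 0.05 indicates good calibration. Keep the test as a descriptive result if wanted, and name the variance form and the number of groups.

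For each outcome and sex, report beside the planned plots:
- the 10-year observed:expected ratio, with observed risk from Kaplan-Meier at 10 years, and its 95% CI;
- the calibration slope with its 95% CI.

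No new pass mark is needed, because the intervals show which sizes of error the data exclude. For ESRD at the planned size, expect about ±8-9% on the ratio and ±0.09-0.11 on the slope. The ratio can be set against the Introduction's figures: over-prediction by 41% is an observed:expected ratio of 1/1.41 = 0.71, and by 23% it is 1/1.23 = 0.81.

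The cost is two extra statistics per model and slightly less favourable wording in the report. No new data are needed.
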